Subjects may also be active in IRB #6654R, 7132R, 7342 (PI [name] on them all) as they are longitudinal studies. However, no study procedures for the other studies will take place while active in the current study. Rather, the other studies are studies which involve an active period, followed by up to two years of longitudinal follow up before procedures are repeated (6654R is the screening/umbrella protocol for all COPE studies). Therefore, subjects will not actually be "active" in more than one study while part of the current study, and therefore subjects will finish this study before moving on to any other studies. Patients will be told about the study by staff at the COPE clinic (IRB #6654R). If interested, the study will be explained in greater detail by a study physician. **Healthy control subjects may also be recruited through 6654R or other Area Psychosis research studies though will only be active in one protocol at a time.**

Inclusion/Exclusion Criteria

Name the subject group/sub sample

Clinical High Risk

Create or insert table to describe the inclusion criteria and methods to ascertain them

Criterion	Method of Ascertainment
1. COPE Patient between the ages of 18-30 (Identified as at clinical high risk for psychosis as defined as a) attenuated psychotic symptoms; or b) brief intermittent psychotic symptoms c) schizotypal disorder or family history of psychotic disorder with recent decline in functioning (30 GAF points))	Structured Interview for Prodromal Syndromes/ Scale of Prodromal Symptoms (SIPS/SOPS)
2. Capacity to provide informed consent	Clinical assessment by research team and independent assessment of capacity
3. Currently using a reliable form of birth control (females and males)	Physician interview

Create or insert table to describe the exclusion criteria and methods to ascertain them

Criterion	Method of Ascertainment
1. Metal implants in body or a history of metal working	Physician evaluation
2. Lifetime diagnosis of asthmatic symptoms within the past 3 years or known sensitivity to contrast agents	Physician evaluation
3. Lifetime diagnosis of renal failure/disease	Physician eval and laboratories
4. Acute neurological, neuroendocrine, or medical disorder including renal insufficiency (CrCl <60mL/min/1.73m ²)	Physician exam, electrolytes, CBC
5. Lifetime diagnosis of hypertension or diabetes or seizure disorder	Physician evaluation
6. IQ < 70	WTAR < 6

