- a. COPE patients (IRB #6654R) Patients will be told about the study by staff at the COPE clinic (IRB #6654R). If interested, the study will be explained in greater detail by a study physician. Patients will provide written informed consent and capacity determined by a licensed, CITI trained MD or PhD psychologist at NYSPI.
- b. Baseline measures (pre-randomization):
 - i. Serum laboratory tests (beta HCG if female, electrolytes, serum BUN/creatinine, CPK, urinalysis, liver function tests, CBC with differential, thyroid function tests); If eGFR <40 mL/min/1.73m² or serum pregnancy test positive, then patients will discontinue the study (exclusion criterion for exposure to gadolinium).
 - ii.a urine toxicology screen
 - iii. general physical exam, including measures of weight, blood pressure, temperature pulse, respiration, EKG.
 - iv. 5cc of blood for DNA analysis
- c. Structural Interview of Prodromal Syndromes (SIPS) to evaluate current prodromal symptoms at time of study entry
- d. SCID to evaluate current psychiatric diagnoses including present of substance abuse
- e. MATRICS, Hollingshead, GFS scales, GAF, CGI, SAFTEE, AIMS, CSSRS, Simpson Angus Scale
- f. MRI with gadolinium contrast and MRS (one hour). All scans will be examined at the image console for gross structural abnormalities such as the presence of mass effects, hydrocephalus, and vascular malformations by study imager and study physician. Since the images obtained in this study are exclusively T-1 weighted, they will not be clinically read, except for screening for gross structural brain abnormalities by neuroradiologist within 7 days of the scan. Should there exist a gross structural brain abnormality, a neuroradiologist will immediately inform the principal investigator. The neuroradiologist will immediately provide an oral report followed by a handwritten or typed note to the PI and the Director of the MRI Unit. A final written transcript of the clinical reading will be provided within two weeks of the oral report. The subject will be informed of the result, post-scan acquisition, by the study PI. Appropriate follow-up with the patient's primary care physician or appropriate sub-specialist and care setting will be immediately arranged for further diagnostic testing/treatment recommendations by study PI in consultation with the neuroradiologist.

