Concomitant Medications: During the trial, no new concomitant psychotropic medications will be permitted of the following classes of medication: antipsychotic or mood-stabilizing medication. Antidepressant and anti-anxiety medication, if needed for clinical management, will be allowed, including lorazepam up to 1 mg daily (hypnotic, or for anxiety) if needed on a PRN basis. If a patient does require lorazepam, they will not take it for 24 hrs prior to MRI scan. If a study participant requires an excluded medication during the course

of the study, they will be discontinued from administration of the POMA, though complete all other study procedures. Other medications that do not interact adversely with POMA will not be changed during the study.

Treatment Design: Enrollment, randomization, blinding, and assessments for safety

Patients will be randomized in a double blind manner to 40mg bid, 80mg bid, 120mg bid, or 160mg bid of POMA. They will be randomized in a 1:1:1:1 ratio. The identity of medications will be blinded having every subject take an equal number of pills (e.g., someone taking 160mg bid will take 4 tablets of 40mg POMA bid, and someone taking 40mg bid will take 1 tab of 40mg POMA bid and 3 identical looking tablets of placebo bid). To minimize risk of nausea, we will taper medications up so that on day 1 subjects will take 40mg bid, on day 2 80mg bid (if at this dose or higher), on day 3 120mg bid (if at this dose or higher), and on day 4 160mg bid.

After subjects have completed their baseline procedures, they will be given a 7 day supply of POMA. They will return on Day 7 and have all baseline measures as described above, with the exception of the SCID and MRI. They will then be given another 7 days of POMA and return on day 14 when they will again receive all baseline measures including MRI with gadolinium injection, but not including the SCID and blood for DNA Analysis.

Medication adherence will be assessed by pill count.

Pregnancy Testing

As above, we will obtain a serum HCG at screening, as well as urine HCG before any MRI scan and on the day that study drug is dispensed if that does not occur on the same day as the first MRI scan.

Follow Up

We will perform a safety check in call 30 days after study participation. We may repeat the safety labs/EKG/physical as necessary after Day 14 if there is a clinical indication to do so.

PK Testing

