5) MRI Imaging: The Magnetic Resonance (MR) scanner uses strong magnetic fields and radio waves to take measurements in the brain. MRI involves lying on a table that slides into a large magnet shaped like a cylinder. Before beginning the procedure, we will determine that patients do not have a pacemaker or any unsafe metallic implants such as an aneurysm clip or heart valve and certain tattoos, and they will be asked to remove any metal or magnetized objects (such as keys, chains, jewelry, retainers, medication patches, hairpins or credit cards). In addition, they will complete a brief interview at the time of study inclusion to determine if they have Asthma or a history of renal failure that may exclude their ability to receive an injection of Gadolinium (see below section). These questions will be repeated on the day of the scan.

For the scanning procedure, they will be asked to lie flat on the back in the MRI scanner for approximately 60 minutes and to remain as still as possible. Some people have reported sensations during MRI scans, such as "tingling" or "twitching" (or, very rarely, a painful sensation), which are caused by changes in the magnetic field that can stimulate nerves in the body. With any MRI scan, on occasion, some people experience nervousness or discomfort due to the scanner's small space and the need to lie still. Except for

pacemakers, some types of metallic implants, and medication patches, we are not aware of any other potentially dangerous interactions or hazards associated with the MRI scan. The MRI scanner also produces a loud noise.

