6) Gadolinium compounds do have side effects, we use Dotarem. One side effect of gadolinium is nausea and vomiting, observed in less than 2 people out of every 100 injected. (1.8% estimate). Dry mouth (less than 2%), dizziness (0.7% up to 3.6%), and headache (2.2% up to 5.8%) are infrequent, yet possible side-effects. An additional side effect is hives, observed in less than 1 person out of every 100 injected with gadolinium. All of these side effects resolve within 20 minutes to several hours. People with asthma or known sensitivities to contrast agents are at increased risk for more serious side rare side effects (less than 1/10,000 injections estimate), such as severe allergic reaction that may result in sudden difficulty breathing, and therefore will not be injected with Gadolinium. Some patients with acute renal failure or end-stage renal disease have developed a serious medical condition known as nephrogenic systemic fibrosis (NSF) after the use of gadolinium for MRI. The primary concern regarding risks to renal function from gadolinium-based contrast agents (GBCAs) is specific to this population of patients who have end-stage renal disease (ESRD) on hemodialysis, or acute, florid, clinical renal failure, and then are exposed to gadolinium. This population of patients is by definition excluded from this study by virtue of medical history and general review of systems. Renal dysfunction as a result of gadolinium in a population without history of end-stage renal disease or acute renal failure has not been described in the medical literature. In a retrospective study conducted at two large medical centers, 74,124 patients were injected with a standard dose of gadolinium (0.1mmol/kg, the same dose used in our research studies) who had no screening for renal function, with a rate of zero/74,124 cases of renal complications (e.g., nephrogenic systemic fibrosis (NSF) or other renal dysfunction) post injection (Prince, Zhang et al. 2008). All 15 cases of NSF that were found in this retrospective study all had severe, clinical renal failure at the time of gadolinium injection. No cases of NSF have been identified in persons with normal renal function or with moderate renal dysfunction.

Regarding this specific risk, the FDA recommends:

1. Become familiar with the patient populations at risk for NSF.
2. Avoid using gadolinium in patients with known risks for developing NSF.

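### The asthma exclusion is ambiguous, and on one reading it admits patients whom the protocol's own gadolinium safeguard says will not receive contrast

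*Protocol*

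**What the plan says.** Four places in the protocol bear on asthma and contrast.

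- **Inclusion/Exclusion Criteria, Clinical High Risk, exclusion 2** excludes "Lifetime diagnosis of asthmatic symptoms within the past 3 years or known sensitivity to contrast agents". The method of ascertainment is a physician evaluation, with no further definition.
- **Risks/Discomforts/Inconveniences, item 6 (gadolinium)** states that "People with asthma or known sensitivities to contrast agents are at increased risk for more serious side rare side effects", gives an estimate of less than 1/10,000 injections, and concludes that they are at risk of severe allergic reaction "and therefore will not be injected with Gadolinium". No time window is attached to asthma.
- **Risks/Discomforts/Inconveniences, item 5 (MRI Imaging)** describes a short interview at study inclusion "to determine if they have Asthma or a history of renal failure that may exclude their ability to receive an injection of Gadolinium", and adds: "These questions will be repeated on the day of the scan".
- **Procedures for minimizing risks, item 5** repeats that interview and its scan-day repetition. Item 6 of the same section lists what the pre-scan medical history should cover (renal disease, diabetes, hypertension) and does not name asthma.

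Contrast is part of every patient's schedule. Study Procedures lists "MRI with gadolinium contrast and MRS (one hour") with the entry assessments, and the Treatment Design text repeats the contrast scan on day 14. The SAP's primary outcome is the change in left CA1 CBV between those two times.

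**The concern.** An exclusion criterion tied to a named safety risk should give the same answer whoever applies it. This one does not. The word *lifetime* and the 3-year limit point to different populations, and the risk text states a third rule with no limit at all.

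The patient affected has an asthma diagnosis in the past and no symptoms in the last 3 years. Depending on the text that staff follow, this patient is excluded at entry, is enrolled and injected at both scans, or is enrolled and then refused contrast. The main thing at stake is that a patient may receive contrast although the protocol says such people will not. A lesser matter is that eligibility may vary between the physicians who assess it.

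**Working it through.** No figure in the plan depends on this point, so the check compares the texts and traces one patient through them.

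**1. Does the exclusion table settle the meaning of *lifetime*?** The next criterion, exclusion 3, reads "Lifetime diagnosis of renal failure/disease", with no window. Exclusion 5 (hypertension, diabetes, seizure disorder) uses the same opening, also with no window. A reader therefore has grounds within the table to take the word literally. Exclusion 2 alone then adds a 3-year limit. The table supports either reading and chooses neither.

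**2. The rules side by side**, for a patient with an asthma diagnosis and no symptoms in the past 3 years:

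| Text | Window | Force | Result |
|---|---|---|---|
| Exclusion 2, lifetime reading | none | excluded | not enrolled |
| Exclusion 2, 3-year reading | 3 years | not excluded | eligible |
| Risks, item 6, read as any asthma | none | absolute | no contrast |
| Risks, item 5, and risk minimisation, item 5 | none | discretionary | left open |

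On the lifetime reading there is no conflict, because the patient never enters. On the 3-year reading the patient is eligible, item 6 read literally forbids the injection, and item 5 leaves it to judgement. If item 6 is not applied, the patient receives contrast at baseline and on day 14: two injections.

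**3. When would the conflict surface?** The asthma interview takes place at inclusion. The MRI counts as a baseline measure, as the day 7 instruction shows: "They will return on Day 7 and have all baseline measures as described above, with the exception of the SCID and MRI". The Treatment Design text hands out study drug only once baseline procedures are finished. The order is therefore inclusion interview, baseline contrast scan with the questions repeated, first drug supply, then the day 14 contrast scan with the questions repeated. If item 6 is enforced at either of the first two steps, the patient is stopped before any study drug. Refusal for the first time on day 14 needs a new disclosure or a changed judgement.

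**4. What happens to the sample?** The SAP plans 3 patients at each of 4 doses: 3 × 4 = 12, which agrees with the protocol's 12 completers. Under its paragraph on adherence, dropouts and missing data, a patient with unusable CA1 values at either visit is replaced. The protocol projects 50 enrolled to obtain those 12, which leaves 50 − 12 = 38 enrolments beyond the completers. A patient refused on day 14 costs one extra enrolment, and that patient has had the drug course and one injection without yielding a primary value.

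**5. Size of the safety exposure.** If the protocol's estimate applies to each injection in this group, two injections give a risk below 2 × 1/10,000 = 1/5,000 per affected patient. The sentence does not make clear whether the estimate refers to people with asthma or to everyone injected. If it refers to everyone, the figure for this group would be higher and is not given. Nor do the documents say how many such patients to expect.

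**The case against.** The strongest reply is that the texts can be made to agree. Exclusion 2 can be read as asthma with symptoms in the past 3 years. The risk text speaks of people who have asthma in the present tense, as does the interview, so both could mean current asthma. The discretionary wording covers asthma and renal history together and fits the physician evaluation named in the exclusion table. This reading is possible, so it would be too strong to call the passages flatly contradictory. However, no passage adopts it, and the unlimited use of *lifetime* in exclusions 3 and 5 works against it. A safeguard should not depend on the reader supplying the link.

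Safeguards also exist. Known contrast sensitivity is excluded without ambiguity. A physician gives the injection and stays through the session and for 15 minutes afterwards, and an epinephrine injector is at hand. Asthma is already asked about at inclusion and at scanning. All of this stands and lowers the severity, but none of it says who is eligible.

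A reader might infer that patients will commonly be dosed for 14 days and then barred from the scan that gives the primary outcome. The documents do not support that as the ordinary course: the interview and the first contrast scan both come before dosing. A reader might also infer that a dose group ends up with fewer than 3 patients. The SAP's replacement rule answers that for the completers.

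**Conclusion.** The point holds as an ambiguity in an eligibility and safety rule. Exclusion 2 has two readings. On the 3-year reading it is narrower than the bar on contrast in the gadolinium risk text, while the interview text is softer than that bar. A patient with remote asthma could be enrolled and injected up to twice against the stated safeguard, and this needs no unusual event, only the 3-year reading.

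Severity is minor. The case rests on patient protection and consistent eligibility. No effect on the estimand, sample size or analysis is shown beyond an occasional extra enrolment.

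Three assumptions are involved. The risk text is taken to mean any asthma diagnosis, which is its literal but not its only sense. The scan-day questions are taken to be asked at both scans. CBV is taken to come from the gadolinium scan, which the protocol implies without saying so outright. The last two bear only on the day 14 case.

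**What to change.** The investigator should reconcile exclusion 2, items 5 and 6 of the risk section, and item 5 of the risk-minimisation section into one asthma rule set by the study's clinicians. The rule should state whether a time window applies, and whether it refers to diagnosis or to symptoms. The same wording should then be used at the existing inclusion interview and in the existing scan-day questions, so that the answer obtained before randomisation is the one applied at both scans. No particular clinical rule is proposed here.

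The cost is a wording amendment to the exclusion table and the risk and risk-minimisation text, with no new procedure. The downside is that a few candidates may be screened out earlier.
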